All subjects will have blood samples drawn for [REDACTED]
[REDACTED]
[REDACTED]
[REDACTED]

Number of Subjects: A total of approximately 152 subjects (38 per treatment group) will be randomized.

Number of Study Sites: Approximately 40 sites in the United States

Test Product(s), Dose, and Mode of Administration: Aldafermin final product will be supplied in pre-filled syringes intended to deliver 0.3 mL containing 0.3 mg, 1 mg, or 3 mg aldafermin for SC injection. Placebo will be provided in volume-matched syringes. Subjects will be instructed to dose aldafermin at home at a similar time each day; however, study drug will be taken in the clinic on study visit days.

Rosuvastatin will be administered for subjects meeting pre-specified LDL-C criteria (statin-naïve subjects) or automatically at Week 2 (statin-experienced). Study-labeled rosuvastatin/matching placebo is over-encapsulated and will be supplied in 5 mg, 10 mg, 20 mg, or 40 mg total daily doses as outlined in [Section 10.1.3](#) of the protocol to manage possible LDL-C increase during aldafermin treatment.

Duration of Treatment: Subjects will sign the Informed Consent Form at the Day -42 Screening Visit and will undergo screening assessments to determine study eligibility. All subjects will be treated with aldafermin or matched placebo for 24 weeks and will be monitored for 6 weeks after completing their final dose of aldafermin or placebo. The total duration of individual subject participation will be approximately 36 weeks.

Statistical Methods: **Analysis Populations:** Subjects will be analyzed using the following analysis populations:

• Intent-to-Treat Population

All randomized subjects will be included in the Intent-to-Treat (ITT) population. The ITT population will be based on randomized treatment if this differs from actual treatment received.

• Safety Population

All subjects who receive at least one dose (full or partial) of study drug will be included in the Safety population. All safety endpoints will be summarized using the Safety population and will be based on actual treatment received if this differs from the randomized/enrolled treatment.

• Full Analysis Population

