2. The primary safety endpoint is frequency, severity, and timing of adverse events (AEs) and serious adverse events (SAEs). Safety and tolerability of aldafermin in subjects with NASH as a function of dose level after up to 24 weeks of treatment with aldafermin will be assessed.

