9.1 Schedule of Study Procedures

The Schedule of Study Procedures is shown in [Table 4](#). The visits should occur as close to the intended dates as possible. However, Weeks 2 and 4 will have a visit window of ± 3 days. Weeks 8, 12, 18, and 24 will have a visit window of ± 7 days. Week 25 will have a visit window of $+3$ days, and Week 30 will have a visit window of ± 7 days. Subjects attending any visits out of windows from Day 1 to Week 24/Early Withdrawal (EOT) visit should be brought back into compliance with the overall study-visit schedule as soon as possible thereafter. Subjects will return to the clinic at Week 25 and Week 30 (1 and 6 weeks after last dose) for a post-treatment response and EOS follow-up visits, respectively.

Subjects who have an LDL-C value of > 100 mg/dL and > 15 mg/dL above their Day 1 value at Week 25 will need to be re-assessed at Week 30. Subjects who have an LDL-C value of > 100 mg/dL and > 15 mg/dL above their Day 1 value at Week 30 will have an additional 4- week follow up visit to confirm their LDL-C value is ≤ 100 mg/dL or ≤ 15 mg/dL above their Day 1 value. Subjects will continue to be followed until their LDL-C value is ≤ 100 mg/dL or ≤ 15 mg/dL above their Day 1 value. Subjects whose LDL-C values are not adequately managed by their maximum tolerated rosuvastatin dose plus ezetimibe will be discontinued from study and an early withdrawal study visit will be completed. The follow up/EOS visit should be scheduled for 6 weeks after the early withdrawal study visit.

Table 4. Schedule of Study Procedures

Study Procedure	(Screening) ^b	D -42	D -28 to -1	D1	W2	W4	W8	W12	W18	W 24/EW (EOT)	W25 (Post-Tx)	W30 (EOS)
Visit Window (Days) ^a					± 3	± 3	± 7	± 7	± 7	± 7	+3	± 7
Informed consent		X										
Demographics		X										
Medical history		X										
Smoking History		X										
Inclusion/exclusion criteria		X		X								
Height		X										
Body weight, BMI, waist circumference		X		X				X		X		X
		■		■	■	■	■	■	■	■	■	■
Alcohol Consumption ^c		X										
12-lead ECG		X		X				X		X		X
Vital signs		X		X	X	X	X	X	X	X		X
Central read of locally performed historical biopsy slides, if available		X										
MRI-PDFF ^d				X				X		X		X
Liver biopsy ^e				X						X		
				■								
Prior and concomitant medications		X	X	X	X	X	X	X	X	X	X	X
Adverse events ^f		X	X	X	X	X	X	X	X	X	X	X
LISSA evaluations				X	X	X	X	X	X	X		
Chemistry (fasted \geq 10 hrs)		X ^h	X ^h	X ^{g,h}	X ^g	X ^g	X ^g	X ^{g,h}	X ^g	X ^{g,h}	X ^g	X ^g

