9.2.12 Lipid Monitoring Assessment 4 Week Follow up Visit Procedures

This visit will be performed 4 weeks after the EOS visit. The following procedures will be performed at this visit:

- Record concomitant medications
- Record AEs

- Obtain blood for 10-hour fasted laboratory sample collection for:
 - Chemistry
 - Lipid panel

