11.1 Definition and Grading Intensity of Adverse Events

An AE is defined as any untoward medical occurrence in a subject of clinical investigational participation administered a pharmaceutical product, whether or not considered drug related. A TEAE is an AE that is reported after a dose of study drug.

AEs include the following:

- Unfavorable changes in general condition
- Subjective or objective signs/symptoms
- Concomitant diseases or accidents
- Clinically relevant adverse changes in laboratory parameters observed in a subject in the course of a clinical study

AEs comprise all disturbances of general health status, subjective and objective disease symptoms (including laboratory abnormalities), and accidents observed in the context of a clinical trial, irrespective of a possible causal relationship with the administration of the trial substance. Events occurring in the framework of a clinical trial during drug-free and post-treatment periods or under placebo are also to be designated as AEs.

All AEs, regardless of how identified (e.g., volunteered, elicited, noted on physical examination), will be recorded throughout the study (i.e., from Screening until Follow-up).

Subjects will be followed for resolution of AEs, by querying the subjects for an ongoing AE until resolved or until any unresolved AEs are judged by the PI to have stabilized or if lost to follow-up. Resolution of all AEs will be promptly documented by the clinic on the subject's CRF.

Any pregnancy diagnosed during the study must be reported immediately to the PI and Sponsor, including pregnancy in female partners of male subjects. The pregnancy will be followed to term and/or outcome and this outcome must be reported to the Sponsor.

Pregnancy, in and of itself, is not regarded as an AE or SAE unless the birth results in a congenital anomaly/birth defect or there is suspicion that the study medication may have interfered with the effectiveness of a contraceptive medication or method.

The PI will rate the severity of AEs using the CTCAE v5 to grade the severity. Each CTCAE v5 term is a Medical Dictionary for Regulatory Activities (MedDRA) Lowest Level Term (LLT). The CTCAE displays Grades 1–5 with unique clinical descriptions of severity for each AE. Not all Grades are appropriate for all AEs. Therefore, some AEs are listed with fewer than five options for Grade selection. Grade 5 (Death) is not appropriate for some AEs and, therefore, is not an option.

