#### **6.2** Adverse Events

Adverse events are collected both for the screening/baseline period pre-treatment (which are referred to as pre-treatment AEs) and for the follow-up period after treatment is initiated (which are referred to as post-treatment AEs). All adverse events will be coded using the Medical Dictionary for Regulatory Activities (MedDRA, v23.0).

Treatment emergent adverse events (TEAEs) are defined as AEs that commence on or after the date (and time if available) of first study drug administration. AEs without an onset date or time will be defined as treatment emergent, except if an incomplete date (e.g., month and year) clearly indicates that the event started prior to the start of first administration of study drug or if the AE stop date indicates that the event started or stopped prior to the start of first administration of study drug.

The severity of an AE is rated by National Cancer Institute (NCI) Common Terminology Criteria for Adverse Events (CTCAE) v5. The relationship of an AE to study drug is made using a four-category system: not related, possible, probable, or definite.

The following summary of TEAEs will be provided.

- An overall summary of any TEAEs, any TEAEs leading to study treatment withdrawal, any serious TEAEs, any Aldafermin-related TEAEs, any Rosuvastatinrelated TEAEs, and death
- TEAEs by PT in descending order of incidence
- TEAEs by primary SOC and PT
- TEAEs by primary SOC, PT and severity (CTCAE grade)
- TEAEs by primary SOC, PT and relationship to Aldafermin
- TEAEs by primary SOC, PT and relationship to Rosuvastatin
- TEAEs leading to study treatment withdrawal by primary SOC and PT
- Aldafermin-related TEAEs leading to study treatment withdrawal by primary SOC and PT
- Rosuvastatin-related TEAEs leading to study treatment withdrawal by primary SOC and PT
- Serious TEAEs by primary SOC and PT

A subject will be counted only once within each preferred term and system organ class in the summary tables. The most severe occurrence of a repeat AE, as well as the most extreme relationship of the AE to the study treatment will be used for these analyses. In addition, for the rosuvastatin-related summary tables, only subjects who received rosuvastatin will be included. All SAEs and AEs leading to study drug withdrawal and death will be provided in separate listings.

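### TEAEs have a start but no end date, so the window depends on Week 30 LDL-C, and no summary covers the timing part of the primary safety endpoint

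*SAP*

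**What the plan says.** SAP 6.2 states that TEAEs "are defined as AEs that commence on or after the date (and time if available) of first study drug administration". It has rules for missing onset dates but no closing boundary. Protocol 11.1 is just as open: "A TEAE is an AE that is reported after a dose of study drug". SAP 6.2 also describes everything after the first dose as collected "for the follow-up period after treatment is initiated (which are referred to as post-treatment AEs)", so time on and time off injection carry the same label.

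Protocol 6.1 reads: "The primary safety endpoint is frequency, severity, and timing of adverse events (AEs) and serious adverse events (SAEs)". SAP 6.2 then lists ten TEAE summaries: an overall table, and tables by preferred term, by system organ class, by severity, by relationship to each drug, by withdrawal (three tables) and by seriousness. None is by onset date, visit or period.

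On collection, Protocol 11.1 says that AEs "will be recorded throughout the study (i.e., from Screening until Follow-up)". For a completer that means Week 30. A subject whose Week 30 LDL-C is above 100 mg/dL and more than 15 mg/dL above Day 1 has a further visit. Protocol 9.2.12 says of it "This visit will be performed 4 weeks after the EOS visit", and AEs are recorded there. Protocol 9.1 adds: "Subjects will continue to be followed until their LDL-C value is ≤ 100 mg/dL or ≤ 15 mg/dL above their Day 1 value".

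**The concern.** A crude incidence is comparable between arms when the period of observation is fixed by design. Here part of it is set by an outcome. Two completers with the same treatment history can have windows of 30 and 34 weeks or more, depending on their Week 30 LDL-C. Protocol 5.4 reports that aldafermin raises LDL-C, so the length of observation may be related to treatment.

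Two further losses follow from the absence of any period structure. Events that begin after the last injection are pooled with events on injection. Events that begin before study rosuvastatin is available (it is first dispensed at Week 2) are pooled with those that begin afterwards, although Protocol 5.4 names the safety of statin co-administration as something the study should evaluate. At stake is whether the trial can report its own primary safety endpoint, which names timing alongside frequency and severity.

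**Working it through.** **Inputs from the documents.** Treatment lasts 24 weeks (Protocol Synopsis, Duration of Treatment: "All subjects will be treated with aldafermin or matched placebo for 24 weeks"). Monitoring after the last dose is 6 weeks, screening starts at Day -42, and total participation is given as about 36 weeks (same place). The extra visit is 4 weeks after EOS (Protocol 9.2.12). Each arm has 38 subjects (SAP 1.1). "Off drug" below would be ambiguous, so I use off injection: statin-experienced subjects continue study rosuvastatin to Week 30.

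**Assumptions, not in the documents.** Constant hazard; 30-week incidence p from 5% to 90%; share f of one arm with one extra visit from 10% to 100%, and none in the comparator.

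**1. The plan's own figure.** 42/7 + 24 + 6 = 36 weeks. This reproduces.

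**2. Composition of the window, from first dose to last AE collection.**
- Completer: 24 + 6 = 30 weeks; off injection 6/30 = 20%.
- Completer with one extra visit: 34 weeks; off injection 10/34 = 29.4%; the window is 34/30 - 1 = 13.3% longer.
- Withdrawal at Week 12, taking the early withdrawal visit as the end of dosing: 18 weeks; off injection 6/18 = 33%.

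**3. How much the pooled figure mixes.** 24-week incidence = 1 - (1 - p)^(24/30).

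| p at 30 weeks | 24-week incidence | Difference (points) | Of 38 subjects |
|---|---|---|---|
| 10% | 8.1% | 1.9 | 0.7 |
| 30% | 24.8% | 5.2 | 2.0 |
| 60% | 52.0% | 8.0 | 3.1 |

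Under these assumptions the mixing is the same in every arm.

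**4. Effect of one extra visit between arms.** Added incidence = f × [(1 - p) - (1 - p)^(34/30)]. For p = 60% and f = 25%: 0.25 × (0.400 - 0.354) = 1.15 points.

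| f | Added person-time (4f/30) | Added incidence over p = 5% to 90% (points) |
|---|---|---|
| 10% | 1.3% | 0.06 to 0.46 |
| 25% | 3.3% | 0.16 to 1.15 |
| 50% | 6.7% | 0.32 to 2.3 |
| 100% | 13.3% | 0.65 to 4.6 |

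At f = 50% the maximum is 0.9 of 38 subjects. Follow-up beyond the first extra visit has no stated length and cannot be sized.

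**5. The opposing mechanism.** Protocol 9.4.14 discontinues subjects whose LDL-C is not adequately managed on their maximum tolerated rosuvastatin dose plus ezetimibe, with EOS 6 weeks after the early withdrawal visit. A Week 12 withdrawal loses 30 - 18 = 12 weeks. As an illustration, 10% of an arm withdrawn at Week 12 loses 0.10 × 12 = 1.2 mean weeks, which exactly offsets 30% of the arm having one extra visit (0.30 × 4 = 1.2 weeks).

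**6. Timing.** The endpoint in Protocol 6.1 has three parts. Frequency is covered throughout SAP 6.2 and severity by the CTCAE grade table. Timing has no table. By contrast, laboratory tests, vital signs, ECGs and injection-site reactions are all summarised by visit (SAP 6.3 to 6.6). Kaplan-Meier estimates appear in SAP 2.2 only where applicable, and no AE time-to-event endpoint is named.

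**The case against.** The strongest reply is that this is a clarification with little numerical consequence. AE recording stops at follow-up, so data collection bounds the window apart from the LDL-C extension. The six weeks after the last injection are scheduled in every arm, and counting them as treatment-emergent is a common choice. With a quarter of one arm attending one extra visit, the differential is under half a subject of 38. Onset dates remain available, because SAP 2.2 lists all subject-level data and SAP 6.2 lists SAEs and withdrawal AEs separately. Injection-site reactions are tabulated by visit, and relationship to rosuvastatin is judged and tabulated on its own.

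Most of this stands, and it limits the size of the point. It is also true that a 42-day cut-off leaves the six off-injection weeks inside the TEAE window; only a period table separates them. What the reply does not answer is that the window's length depends on a post-randomisation laboratory value, that the further LDL-C follow-up has no end, and that a listing is not a summary of a named endpoint component.

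A reader might infer that the extra follow-up falls mainly on aldafermin subjects. That is plausible, but the trigger is identical in all arms, it is measured about six weeks after the last dose, and no rate by arm is given. A reader might also take Weeks 0 to 2 as free of rosuvastatin. They are free only of study rosuvastatin: Protocol 8.1 lets statin-experienced subjects take their own statin through Week 2, including rosuvastatin up to 20 mg/day.

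**Conclusion.** The point holds for the definition and for the missing summary. Neither document closes the TEAE window, LDL-C-triggered follow-up extends it for some subjects only, on- and off-injection events are pooled, and none of the ten TEAE summaries reports timing.

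The effect between arms is probably small, 0.16 to 1.15 points under the 25% scenario, given the constant-hazard assumption and an assumed share of extra visits. It would be tempting to conclude that the plan makes aldafermin look worse. The documents do not support a direction, because the extra visits lengthen windows while LDL-C discontinuations shorten them, and neither rate is given. Nor is timing information lost: it is in the listings but not summarised. The change is worth making before database lock because it is cheap and lets the trial report its primary safety endpoint in full.

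**What to change.** In SAP 6.2:

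- Define TEAEs as onset from first dose through a fixed number of days after the last aldafermin or placebo injection, the same in all arms. Use 42 days to match the planned EOS, or 49 to cover the +7-day Week 30 visit window, and state which. Anchor to the injection explicitly, since some subjects continue study rosuvastatin after it.
- List AEs with later onset separately.
- Add one table of TEAEs and serious TEAEs by arm and onset period: first dose to the Week 2 visit (before study rosuvastatin); Week 2 visit to last injection; after last injection to the cut-off. Use subjects at risk in each period as the denominator.

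A common cut-off removes the LDL-C-triggered extension. It does not equalise windows shortened by early withdrawal, which is why the at-risk denominators are needed.

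The cost is a wording change and one more set of tables. AE onset dates and first and last dose dates are already collected, and no study procedure changes. The downside is that late events move from the tables to a listing. Protocol Section 12 lets the SAP override that section in case of discrepancy. The TEAE definition in Protocol 11.1 lies outside it, so the SAP should record the difference as a deviation from the protocol.

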5.4 Study Rationale

This is a Phase 2b study being conducted to evaluate the efficacy and safety and tolerability of aldafermin in patients with histologically confirmed NASH upon treatment for 24 weeks. The doses selected are supported by both the nonclinical and clinical data generated to date and are within the current safety margins in both monkeys and mice obtained in the GLP 26-week toxicology program. Based on efficacy of aldafermin observed NASH patients (Study 15-0105 [Section 5.2.2](#)), the selected doses of 0.3 mg, 1 mg, and 3 mg of aldafermin are expected allow a balance of optimizing biologic activity versus safety and tolerability in the studied population.

Additionally, while the efficacy obtained with 12 weeks of aldafermin treatment in [Study 15-105](#), as measured by non-invasive assessment and liver histology, equals or exceeds the effects seen with available treatments per the current clinical guidelines and mid- and late-stage investigational agents that have been studied in Phase 2 and is encouraging, longer exposures are desirable in the further development of the molecule. Recent publications endorsed by the FDA have supported that 24 weeks is a sufficient duration to determine histologic response, depending on the mechanism of action of the drug being tested. Therefore, this study will evaluate the efficacy of aldafermin at 24 weeks.

Moreover, given that aldafermin has been shown to cause as increase serum levels of total and LDL-C cholesterol in normal volunteers ([Study 12-0101](#)) and T2D patients ([Study 13-](#)

0102), 5, 10, 20, and 40 mg of rosuvastatin will be studied in this study to further evaluate co-administration of a statin on lipid levels, safety, and tolerability in a larger population of aldafermin-treated subjects.

[REDACTED]

[REDACTED]

[REDACTED]

6 Study Objectives

6.1 Primary Objectives and Endpoints:

The primary objectives are to evaluate the efficacy, safety and tolerability of aldafermin based on liver histology at 24 weeks versus placebo.

1. The primary efficacy endpoint is the histologic response defined as an improvement in liver fibrosis by ≥ 1 stage by NASH Clinical Research Network (CRN) criteria with no worsening of steatohepatitis at Week 24 compared with baseline.

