LDL-C will be evaluated at Weeks 2, 4, 8, 12, and 18 in all subjects for possible increases in lipid levels associated with aldafermin administration. Rosuvastatin will be started in subjects meeting specific LDL-C level criteria at Week 2. Rosuvastatin and matched placebo are over-encapsulated to maintain the blind at the sites and with the sponsor study teams. Initiation and ongoing dose adjustments of rosuvastatin/matched placebo will be managed by an unblinded third-party medical monitor and through the [REDACTED] The sponsor and study sites will be blinded to LDL-C values and the specific rosuvastatin dosing decisions as outlined in [Section 9.4.14](#). Subjects who have not achieved an adequate response or cannot tolerate rosuvastatin as defined in [Section 9.4.14](#) will be considered for the addition of ezetimibe as second-line lipid management therapy. Ezetimibe 10 mg tablets can be administered with or without food at the same time as rosuvastatin and aldafermin. Subjects whose LDL-C values are not adequately managed by their maximum tolerated rosuvastatin dose plus ezetimibe will be discontinued from study and an early withdrawal study visit will be completed. The follow-up visit/EOS should be scheduled for 6 weeks after the early withdrawal study visit. The specific rosuvastatin dosing algorithm is outlined in detail in [Appendix 3](#).

Rosuvastatin or matching placebo will be dispensed at each study visit through Week 18 (statin-naïve) or Week 24 (statin-experienced). If the subject is taking statins, evaluate tolerability and continue therapy to Week 24 if statin naïve or Week 30 if statin experienced.

All subjects will return to the clinic at Week 25 for post-treatment LDL-C assessment. Subjects who have an LDL-C value of >100 mg/dL and >15 mg/dL above their Day 1 value at Week 25 will be re-assessed at Week 30. Subjects who have an LDL-C value of > 100 mg/dL and > 15 mg/dL above their Day 1 value at Week 30 will have an additional 4- week follow-up visit to confirm their LDL-C value is \leq 100 mg/dL or \leq 15 mg/dL above their Day 1 value.

The study visit at Week 24 will be the aldafermin EOT clinic visit and subjects will return to the clinic at Weeks 25 and 30 (or at 1 and 6 weeks after last dose of aldafermin) for a post-treatment response and EOS follow-up visits. Subjects are required to undergo MRI performed during Screening Day -28 and at Weeks 12, 24 / Early Withdrawal (EOT), and 30 (EOS) visits.

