9.4.14 Lipid-Lowering Therapy Assessment

LDL-C will be evaluated at all study visits for possible increases in lipid levels associated with aldafermin administration. Rosuvastatin will be started in subjects meeting specific LDL-C level criteria at Week 2. Rosuvastatin and matched placebo are over-encapsulated in bottles of 35 capsules ([Section 10.4.2](#)). Initiation and ongoing dose adjustments of rosuvastatin will be managed by an unblinded third-party Medical Monitor and through the [REDACTED]. Lipid levels will be blinded to the sponsor and site. Initiation and dose adjustments will be determined by the lipid levels collected at Weeks 2, 4, 8, 12, and 18. LDL-C samples will be analyzed and reported to the third-party Medical Monitor. Bottles of rosuvastatin and/or matching placebo will be dispensed at each study visit through Week 18 (statin naïve) or Week 24 (statin experienced) as instructed through [REDACTED] [REDACTED] [REDACTED]. The subject will be sent home from their clinic visit with the IVRS assigned bottle(s) and instructed to refrain from dosing until told from which bottle or bottles to dose by the study site. The third-party Medical Monitor will review the LDL-C level and assign the dose of rosuvastatin [REDACTED] [REDACTED] based on the dosing algorithm ([Appendix 3](#)). The site will subsequently communicate to the subject the assigned bottle(s) and dosing should be immediately initiated.

Subjects who have not responded adequately to rosuvastatin (defined as >100 mg/dL and > 15 mg/dL above their Day1 LDL-C level), and who are currently receiving their maximum tolerated rosuvastatin dose, will be considered for additional lipid-lowering therapy (ezetimibe). The third-party Medical Monitor will contact the site regarding any subject meeting this criterion. Ezetimibe will be prescribed and taken as second-line treatment per investigator judgement and approval from the Sponsor Medical Monitor or designee. Rosuvastatin therapy should be continued as assigned. Ezetimibe should be used in accordance with the FDA-approved package insert ([Appendix 7](#)). The subjects should also continue aldafermin/matched placebo through EOT as assigned.

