11.2 Criteria for Determining Relationship to Study Drug

The PI will make a blinded determination of the relationship of the AE to aldafermin/matched placebo, rosuvastatin/matched placebo or ezetimibe (as applicable). All determinations of relationship will be made using a four-category system (not related, possible, probable, or definite) according to the following guidelines:

- **NOT RELATED** = an AE that does not follow a reasonable temporal sequence from administration of the drug and that can be reasonably explained by other factors, including underlying disease, complications, concomitant drugs, or concurrent treatment;
- **POSSIBLE** = an AE that follows a reasonable temporal sequence from the administration of the drug (including the course after withdrawal of the drug) and that cannot be excluded as being possibly caused by the drug (e.g., existence of similar reports attributed to the drug and/or its analogues; reactions attributable to the pharmacological effect of the drug), although other factors such as underlying disease, complications, concomitant drugs, or concurrent treatment are presumable;
- **PROBABLE** = an AE that follows a reasonable temporal sequence from administration of the drug (including the course after withdrawal of the drug) and that can be excluded as being possibly caused by other factors, such as underlying disease, complications, concomitant drugs, or concurrent treatment.
- **DEFINITE** = an AE that follows a reasonable temporal sequence from administration of the drug (including the course after withdrawal of the drug), follows a known or hypothesized cause–effect relationship, and (if appropriate) satisfies the following:
 - Positive results obtained in drug sensitivity tests
 - Toxic level of the drug present in blood or other body fluids

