Low density lipoprotein cholesterol (LDL-C) will be evaluated at Weeks 2, 4, 8, 12 and 18 in all subjects for possible increases in lipid levels associated with Aldafermin administration. In statin naïve subjects, rosuvastatin will be started in subjects meeting specific LDL-C level criteria at Week 2. In statin experienced subjects, rosuvastatin (10mg OD in non-Asians and 5mg in Asians) will be started at Week 2. Rosuvastatin and matched placebo are over encapsulated to maintain the blind at the sites and with the sponsor study teams. Initiation and ongoing dose adjustments of rosuvastatin/matched placebo will be managed by an unblinded third-party medical monitor and through the ....... The sponsor and study sites will be blinded to LDL-C values and the specific rosuvastatin dosing decisions as outlined in Section 9.4.14 of the protocol. Subjects who have not achieved an adequate response or cannot tolerate rosuvastatin as defined in Section 9.4.14 of the protocol will be considered for the addition of ezetimibe as second-line lipid management therapy. Ezetimibe 10 mg tablets can be administered with or without food at the same time as rosuvastatin and Aldafermin or as monotherapy. Subjects whose LDL-C values are not adequately managed by their maximum tolerated rosuvastatin dose plus ezetimibe will be discontinued from study and an early withdrawal study visit will be completed. The follow-up/end-of-study (EOS) visit should be scheduled for 6 weeks after the early withdrawal study visit.

Rosuvastatin or matching placebo will be dispensed at each study visit through Week 18 (statin-naïve) or Week 24 (statin experienced). If the subject is taking over-encapsulated rosuvastatin or matched placebo, evaluate tolerability and continue therapy to Week 24 if statin naïve or Week 30 if statin experienced.

All subjects will return to the clinic at Week 25 for post-treatment LDL-C assessment. Subjects who have an LDL-C value of >100 mg/dL and > 15 mg/dL above their Day 1 value at Week 25 will be re-assessed at Week 30. Subjects who have an LDL-C value of > 100 mg/dL and >15 mg/dL above their Day 1 value at Week 30 will have an additional 4-week follow-up visit to confirm their LDL-C value is  $\leq$  100 mg/dL or  $\leq$  15 mg/dL above their Day 1 value.

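### Rosuvastatin-related adverse-event tables are limited to rosuvastatin recipients, so their by-arm percentages are not randomized comparisons and the placebo-capsule background rate is not shown

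*SAP*

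**What the plan says.** SAP 6.2 lists the TEAE summaries and then adds that "for the rosuvastatin-related summary tables, only subjects who received rosuvastatin will be included". The tables concerned are those by relationship to rosuvastatin and of rosuvastatin-related events leading to withdrawal. The overall summary also has a line for any rosuvastatin-related TEAE, and the text does not say whether the restriction reaches it. SAP 2.1 assigns all safety endpoints to the safety analysis set, and protocol 12.6 assigns all safety analyses to the Safety population.

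There are two routes to active rosuvastatin. The protocol Synopsis (test products) states: "Rosuvastatin will be administered for subjects meeting pre-specified LDL-C criteria (statin-naïve subjects) or automatically at Week 2 (statin-experienced". SAP 1.1 agrees: "In statin naïve subjects, rosuvastatin will be started in subjects meeting specific LDL-C level criteria at Week 2", and "In statin experienced subjects, rosuvastatin (10mg OD in non-Asians and 5mg in Asians) will be started at Week 2".

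On the drug's effect, protocol 5.4 says that "aldafermin has been shown to cause as increase serum levels of total and LDL-C cholesterol in normal volunteers"; the same sentence also names patients with type 2 diabetes.

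On the capsules, protocol Section 7 says: "Rosuvastatin and matched placebo are over-encapsulated to maintain the blind at the sites and with the sponsor study teams". Protocol 9.4.14 says: "The third-party Medical Monitor will review the LDL-C level and assign the dose of rosuvastatin". Protocol 11.2 says: "The PI will make a blinded determination of the relationship of the AE to aldafermin/matched placebo, rosuvastatin/matched placebo or ezetimibe (as applicable".

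**The concern.** Whether a statin-naive subject appears in these tables is settled after randomization, by a laboratory value that the randomized drug is stated to raise. Established statin users, who enter in every arm, may make up most of the placebo column. Newly started subjects may make up much of the higher-dose columns. If new starters report more capsule-attributed events, the columns will differ even when aldafermin adds nothing.

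The second issue is attribution. Investigators judge relationship to the capsule without knowing its content, so some events will be attributed to capsules that hold no drug. The restriction removes the subjects in whom that could be seen.

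Protocol 5.4 gives further evaluation of the safety and tolerability of statin co-administration as a reason for studying rosuvastatin here. These are the planned tables that show attribution to it, and a reader could take a difference between columns for an interaction with aldafermin.

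**Working it through.** The documents give no figure for these tables, so there is nothing to reproduce. The check is a reading of the text and an illustration of how the mix acts.

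**Text**

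- The restriction is explicit, and it departs from SAP 2.1 and protocol 12.6.
- The experienced route depends on a baseline feature, apart from dropout before Week 2. The naive route depends on on-treatment LDL-C.
- Capsule content follows LDL-C through the third-party monitor. It is not randomized.
- SAP 6.2 does not say that its tables are by treatment group. I assume that they are, as in SAP 6.1 and 6.3 to 6.6.

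**Illustration**

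The arm size of 38 comes from SAP 1.1. Everything else is assumed, because the documents give neither the statin-experienced share nor the rate at which the LDL-C criteria are met, and the algorithm in protocol Appendix 3 is not shown. Let e be the experienced share, equal across arms; c the share of naive subjects who meet the criteria; and r_e and r_n the risks of a capsule-attributed event in experienced subjects and naive starters, equal across arms.

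- Recipients = 38 × [e + (1 − e)c]
- Table rate = [e·r_e + (1 − e)c·r_n] / [e + (1 − e)c]

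Worked case: e = 40%, c = 10% on placebo and 80% on 3 mg, r_e = 3%, r_n = 10%.

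- Placebo: 38 × (0.40 + 0.06) = 17.5 recipients, of whom 0.06/0.46 = 13% are naive. Rate = (0.012 + 0.006)/0.46 = 3.9%.
- 3 mg: 38 × (0.40 + 0.48) = 33.4 recipients, of whom 0.48/0.88 = 55% are naive. Rate = (0.012 + 0.048)/0.88 = 6.8%.
- In subjects with an event: 17.5 × 0.039 = 0.7 on placebo and 33.4 × 0.068 = 2.3 on 3 mg.

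Range: e of 30%, 40% and 50%, each with c (placebo, 3 mg) of (0, 60%), (10%, 80%) and (20%, 90%).

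| | Placebo | 3 mg |
|---|---|---|
| Recipients of 38 | 11–23 | 27–36 |
| Subjects left out | 15–27 | 2–11 |
| Table rate | 3.0–5.2% | 5.6–7.7% |

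Two conditions remove the gap:

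- Equal c. With c = 30% in both arms and e = 40%, both have 38 × 0.58 = 22.0 recipients and a rate of (0.012 + 0.018)/0.58 = 5.2%.
- Equal risk. With r_e = r_n = 5%, both arms show 5.0% and only the denominators differ.

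**Does the full Safety set cure it?**

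Take the worked case, assume that everyone not on active rosuvastatin takes placebo capsules, and assume 3% attribution to those.

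- Placebo: 0.018 + 0.54 × 0.03 = 3.4%.
- 3 mg: 0.060 + 0.12 × 0.03 = 6.4%.

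The ratio is 0.0636/0.0342 = 1.86, against 0.0682/0.0391 = 1.74 in the restricted table. The full-set comparison is randomized, but it still carries the difference in how often rosuvastatin was started.

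**The case against.** The strongest defence is that tables of attributed events in exposed subjects are a usual descriptive display. SAP 6.2 plans no test on them. Its unrestricted tables (by preferred term, by system organ class, by severity, serious, and leading to withdrawal) keep a randomized comparison of all events, muscle and liver terms included, and SAP 2.2 lists all subject-level data. Protocol 5.4 speaks of statin co-administration in aldafermin-treated subjects, which is a question about exposed subjects, and it is rationale rather than a Section 6 endpoint. All of this stands, and it limits the harm to the rosuvastatin-attribution tables. It does not make those columns comparable, and the unrestricted tables do not show rosuvastatin attribution.

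A reader might infer three stronger things that the documents do not support.

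- That the table population is created by aldafermin's LDL-C effect alone. Statin-experienced subjects enter in every arm.
- That a placebo-capsule control is thrown away. The capsule is a blinding device. On the stated rules its takers are naive subjects who did not meet the LDL-C criteria, so the same post-randomization process selects them. They give a descriptive background rate only.
- That events before the first capsule will contaminate the tables, because TEAEs count from the first study-drug dose. Protocol 11.2 requires a reasonable temporal sequence from administration before an event is rated related, which largely covers this.

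Nor should established users be pictured as uniquely tolerant. The criterion is at least 3 months on a listed statin, not necessarily rosuvastatin, and exclusion 21 removes known statin intolerance from all subjects.

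**Conclusion.** The point holds in a limited form. The restriction departs, without explanation, from the plan's own Safety-set rule. By-arm percentages in the rosuvastatin-related tables are not protected by randomization, because entry of statin-naive subjects depends on an on-treatment value that aldafermin is stated to raise. The restriction also hides the only within-trial background rate for capsule-attributed events.

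The size is unknown. The illustrated gap rests wholly on assumed shares and on an assumed higher risk in naive starters, and it corresponds to about 1 subject against about 2. It shows the direction and mechanism and is not an estimate for this trial. The efficacy analyses and the unrestricted TEAE tables are unaffected. This is a cheap improvement to descriptive tables; the documents do not support calling the safety evaluation invalid.

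**What to change.** In SAP 6.2:

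1. Keep the recipients-only tables, state that they are not comparative between arms, and split them by baseline statin status (experienced or naive).
2. Add the same rosuvastatin-related tables on the full Safety set by arm, with columns for active rosuvastatin and for placebo-only capsules.
3. Footnote the added tables: the by-arm comparison reflects aldafermin together with how often rosuvastatin was started, and the placebo-only column is a descriptive background, not a randomized control.
4. State whether the overall-summary line for any rosuvastatin-related TEAE is restricted.

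The cost is SAP wording and a few more columns, with no new data collection. Some cells will be small. In the worked case there are about 38 × 0.6 × 0.1 = 2.3 naive rosuvastatin users on placebo and 38 × 0.6 × 0.2 = 4.6 placebo-only subjects on 3 mg, so counts should be shown beside percentages.
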